A large body of studies exists on the potential applicability of BCG and SCG in clinical practice. For instance, SCG records changes in the ventricular wall motion and compliance after an ischaemic event to a similar extent than an ECG (12), and when combined with an ECG, the accuracy of detecting physiologically significant coronary artery disease is greater than with an ECG recording alone (13). BCG was successfully used in automatic detection of atrial fibrillation (14), and to predict adverse clinical outcome in patients with heart failure (15).

Apart from the clinical setting, BCG and SCG have been used to analyse cardiac function in a microgravity environment. The first 3D-BCG recordings were made during the 4th expedition on the Saluyt-6 orbital station by the Soviets (16), as well as during the Spacelab mission in 1993 (17). 3D- BCG was also used to assess cardiac function (pre-ejection period (PEP)) and left ventricular ejection time (LVET)) on 5 healthy volunteers during the European Space Agency parabolic flight campaigns (18).

SCG and BCG signals: from parameters recording to biological interpretation

The SCG records the base-to-apex rotational movements transferred to the chest wall in the form of micro-vibrations. Several parameters of biological interest can be derived from SCG signals, especially the amplitude and temporal signals. The amplitude signals are related to left ventricular pressure (19), stroke volume and aortic blood pressure (20). Temporal signals provide information about ventricular function: namely a) PEP, a marker of cardiac contractility, b) LVET, c) the PEP/LVET ratio, a heart rate independent parameter and d) the isovolumic relaxation time (IVRT), which reflects the cardiac performance during the diastolic phase of the cardiac cycle (21). The BCG records also several waveforms, three of which are likely

of main importance for sleep apnoea monitoring: namely the “I”, “J” and “K” waves (7, 8). These waves are elicited by the ventricular contraction which occurs after the QRS complex on the ECG. They represent the body movements in response to the cardiac blood ejection (22). Should the thoracic aorta be simplified into an ascending and a descending tube, on whom blood pressure and volume flow rate forces act in opposite directions, then the BCG waveforms represents the sum of those forces (8). Various cardiovascular parameters can be estimated from the BCG signal, and are shortly presented below. The J wave of the BCG represents the point of highest amplitude in the BCG waveform; heart rate can be determined by the time interval between consecutive J peaks, the J-J intervals (23). Various algorithms can assess heart rate from BCG signals (24-28). Also, heart rate variability, a non-invasive tool to assess cardiac sympathetic and parasympathetic modulation (29), can be calculated from BCG peak intervals, without the need of RR interval calculations obtained from ECG recordings. Changes in BCG waveforms amplitude are related to stroke volume (SV) and cardiac output (CO) modifications in healthy subjects (30, 31). Finally, similarly to SCG, BCG measurements provide an estimation of the PEP (32, 33), and the LVET which indicates the percentage of the cardiac cycle devoted to ejection as compared to ventricular filling (34, 35).

Sleep disordered breathing and their cardiovascular impact: why detect them?

Sleep apnoea syndrome is a common chronic respiratory disease characterised by cyclic airflow cessations during sleep. Clinically, they are classified in three entities: obstructive, where the airflow cessation is due to upper airways collapse; central, where the airflow cessation arise from a central lack in driving to the breathing muscles with no compensatory respiratory efforts; mixed, characterised by an initial central event followed by an obstructive one. Nowadays, up to 24% of men and to 9% of women aged 30 to 60 years disclose already an asymptomatic and underdiagnosed sleep disorder breathing (SDB) (36). Its current high prevalence will supposedly increase in the future years, as a result of the obesity pandemic in an ageing population. SDB is a potential cardiovascular risk factor (37). A patent causal relationship between SDB and cardiovascular disease has not been clearly established until now, but several chronic patho-physiological mechanisms could make sense in supporting such a link. Intermittent hypoxaemia, due to cycled upper airway collapse, is responsible for abnormal sympathetic activation (38), endothelial dysfunction (39), oxidative stress (40) and inflammation (41), all of which are related to cardiovascular illnesses, especially hypertension (42), atherosclerosis (43), cardiac arrhythmias (44), heart failure (45), and coronary artery disease (46). SDB is, likewise, positively correlated with an increased morbidity and mortality in the cardiovascular population (47, 48) and seems to be an independent predictive factor in cardiovascular mortality after an acute coronary syndrome (49).

Moreover, the classical profile of patients at risk of having SDB (obese subjects, Pickwickian syndrome) has changed in the past year, so that there are new categories of patients who should be evaluated for sleep apnoea, above all those with cardiovascular co-morbidities (50).

Sleep disordered breathing and kino-cardiography: a new and promising tool for unobstrusive recording of SDB and its impact on the cardiovascular system.

Complete laboratory polysomnography (PSG) is the gold standard to diagnose SDB (50, 51). However, it is an expensive, time-consuming and uncomfortable tool, limiting its wide-spread use despite the high frequency of SDB in the general population. However, considering the high prevalence of SDB in the general population and the change in the profile of patients at risk of SDB and then, who should be evaluated for, there is growing interest in the research of alternative strategies to reach the most of patients at possible. A number of home sleep testing devices has been proposed over years to screen patient at risk of SDB, but according to the guidelines, they are NOT recommended for patients with cardiovascular comorbidities (50). Moreover, the devices available nowadays do not provide any information on the direct impact of the apnoea on the cardiovascular system.

Nevertheless, taking into account the high prevalence of SDB and the limited accessibility of expensive sleep testing *on one side* and, *on the other side*, the marked recent technological advances in SCG and BCG technologies *as well as* the peculiar hemodynamic characteristics of sleep apnoea episodes, we wish to test

the hypothesis that modern SCG and BCG recordings can provide an highly accurate assessment of sleep apnoea, and evaluate the effects of nCPAP therapy.

There are several reasons to believe that the implementation of recent improvements in SCG-BCG will allow a precise quantification of such sleep-related events:

- 1) The cyclic pharynx collapses during sleep are associated to brain arousal, intrathoracic pressure swings (the so called ‘Mueller – manoeuvres’), and intermittent episodes of hypoxaemia and re-oxygenation (45). When respiration resumes, the cardiac output faces a markedly increased peripheral sympathetic activity, leading to sudden rises in systemic blood pressure, and reflex reductions in heart rate, while the opposite occurs during the periods of respiratory collapse. As explained above, these changes are likely to induce marked modifications in the amplitude and temporal recording assessed by SCG recordings, as well as in the “I”, “J” and “K” waves obtained from the BCG.
- 2) Previous studies which tested if BCG can detect sleep disturbances are encouraging, despite using remote techniques: Da Woon et al. used an unobtrusive polyvinylidene fluoride film sensor on a bed mattress to record BCG signals in a selected group of 10 OSA patients and 10 controls (52, 53). They calculated heart rate (HR) and heart rate variability (HRV) from J-J BCG interval and detected awakening periods in OSA patients with an accuracy of 97%. *The authors could however not determine why sleep was fragmented with this technique.* Zaho et al. also used a micro-movement sensitive bed mattress in subjects with a BMI < 35 kg/m² and no other concomitant cardiorespiratory disease (54). HRV was also retrieved from J-J BCG interval. However, *only selected periods of sleep were analysed for sleep-breathing events, a surrogate marker for obstructive, but not central apnoea.* Detection of these events was nevertheless achieved with a sensitivity of 98%, a specificity of 94%, and an accuracy of 98% (55). Last, Dehkordi et al. showed that it was possible to distinguish between central and obstructive events by recording acceleration from the suprasternal notch, the thorax and the abdomen (56). The subjects investigated were however *only normal volunteers* who performed several voluntary breaths hold in the presence of an oral nasal flow detector.
- 3) The unique expertise of our research team is that we are capable to record SCG and BCG signals in 3 dimensions (57, 58), both linearly and rotationally (16-18). While the above mentioned studies (52-56) assessed BCG changes only in a horizontal plane (x and y axis), which is not representative of the complex cardiac mechanic, we are capable to record these changes in a third anteroposterior dimensions (z axis). This is important because of the anterior-posterior direction of the aortic arch. In addition, as emphasized in the introduction of this research proposal, an important component of the body reaction to the heart movements is rotational, which we are capable to record in 3 dimensions. Overall the combined SCG and BCG 3D-linear and 3D-rotational signals represent 6 degrees of freedom (DOF) while past BCG had only 2-DOF. For simplicity, this 6 DOF signal combination will be designated as Kino-cardiography (KCG) recordings in this research proposal. We anticipate that the unique KCG properties will considerably increase our detection capability of obstructive and central apnoea, as compared to previous studies.

2. Aims and hypothesis tested

The main hypothesis tested in our study is that KCG provides sensitive and accurate measures of obstructive and central apnoea as compared to state-of-the-art polysomnography. Our secondary hypotheses are related to modifications in the SCG and BCG parameters during the apnoea and the effects of nCPAP therapy: we believe that the KCG signals are profoundly affected by the apnoea and they are reversed to the normal baseline with the CPAP. These hypotheses will be tested through a series of studies in normal volunteers and patients.

1-MAIN HYPOTHESES:

Group A. After a fine tuning period of the KCG signal post processing to maximise the sensitivity and specificity of voluntary apnoea detection in health subjects, we will start the first validation study. In 46 healthy volunteers, a computer program will generate random instructions of periods of normal breathing, voluntary end-expiratory breathing cessations periods (as surrogate of central apnoea) and Muller's manoeuvre (as surrogate of obstructive apnoea). Meanwhile, the KCG will record the above-mentioned parameters. The number and duration of voluntary central and obstructive apnoea will be assessed in the KCG recordings, not knowing how many were actually generated by the computer program. We will also record the ECG, heart rate, beat to beat non-invasive blood pressure (Finometer), humeral blood pressure (Dinamap), ventilation, end-tidal CO₂ (AD instruments), O₂ saturation (Nellcor), cardiac output (CO) (Philips).

Group B. In patients suspected of sleep apnoea and admitted to the sleep unit of the Erasme hospital to perform sleep test as required by their medical condition, we will simultaneously record KCG and PSG and qualitatively compare the data. Bland-Altman plots will analyse the agreement between the sleep recordings obtained with the two methods. Peculiar attention will be paid to the accuracy of the detection of obstructive *versus* central *versus* mixed apnoea, of awakenings, and of the time spend in bed. In this second phase of the study, we plan to record these parameters only in selected patients, who will not disclose marked abnormalities which could hamper the reliability of the KCG recordings, namely moderate or severe valvular disease, permanent atrial fibrillation or frequent premature contractions, atrio-ventricular conduction disturbances, medications which reduce heart rate and heart rate variability (beta blockers, anti-arrhythmic drugs, calcium blockers, ...), cardiac rhythm driven by a pace maker, heart failure of any origin, neurological diseases responsible for abnormal movements (restless leg syndrome, Parkinson disease, ataxia ...).

Group C. In patients with a diagnosis of OSA, we will determine if KCG is capable to reliably assess the efficacy of the nCPAP therapy in comparison to simultaneous PSG recording. Ongoing adjustment in CPAP therapy pressure during the night, and its effect on cardiovascular haemodynamic assessed by the KCG, will be taken into account as well. The capability of the technique to detect changes in sleep quality will be tested both *within* subjects (before vs. after nCPAP therapy in the same patient) as well *among* the subjects investigated. The same restriction in the recruitment of the subjects of group B will be applied for the present group.

Group D. After validation of the three previous steps, we plan to extend the recordings on 100 unselected consecutive patients who will undergo PSG recordings because of complains of sleep apnoea. This will validate the clinical usefulness of KCG recording for the detection of sleep apnoea even in patients with multiples co-morbidities.

2-SECONDARY HYPOTHESES

We will test the hypothesis that the apnoeic events profoundly affected the KCG signals (PEP, LVET and PEP/LVET ratios). These parameters are affected by changes in cardiac pre- and after- load and sympathetic activity on myocardial contractility. Similarly, we plan to test the hypothesis that the isovolumic relaxation time (IVRT), an index of diastolic performance during the cardiac cycle, will be altered during the obstructive apneas, because marked variation in intrathoracic pressure result in large increases in LV transmural gradient and thereby reduce LV compliance. CPAP therapy should markedly reduce the nighttime variability in these parameters.

We will also asses the R-J interval which is related to blood pressure and determine if this parameter rises during the apneas and arousals when sympathetic activity is increased. Determination of the J-J intervals and the corresponding HRV, which is under strong autonomic control, should also present distinct changes in OSA patients, as compared to subjects receiving efficacious nCPAP therapy.

Last, breathing effort variations will be assessed. This refers to the mechanical interaction between respiration and KCG signals when sleep apnea occurs, independently from an autonomic nervous modulation of heart rate variability: when the obstructive apneic event occurs, the airflow decreases, which result in a

breathing effort thereafter. We will test the hypothesis that these respiratory abnormalities are readily detectable by the KCG.

3. Methods

Study design and recruitment, expertise of the research group

Study A is an interventional pre-study on voluntary breath holding on healthy subjects. The parameter taken into consideration for sample size calculation in this group is the total (linear and rotational) systolic kinetic energy of the SCG (S_{sys_kin}) and the rolling ratio between the mean value and the standard deviation of this parameter: $H = \text{Mean}(S_{sys_kin}) / \text{Std}(S_{sys_kin})$. H discriminated voluntary obstructive apneas from episodes of normal respiration in a healthy volunteer ($H = 1.1627$ and 0.2308 , respectively). The sample size is determined according to: $2 \cdot (Z_{\alpha} + Z_{1-\beta})^2 \cdot \sigma^2 / \Delta^2$, where $\alpha = 5\%$ is the accepted error, leading to $Z_{\alpha} = 1.96$ (2-sided); $\beta = 95\%$ is the power of the study, leading to $Z_{1-\beta} = 1.64$; σ is the estimated standard deviation of H; Δ is the estimated effect of obstructive sleep apnea on H in patients. σ ($H_{baseline}$) = 0.1247 was obtained by H determinations on a group of healthy subjects who were breathing regularly. The difference in H during regular breathing and voluntary obstructive apnea, divided by 10 (because voluntary apneas may have induced larger changes than those experienced by patients) is $\Delta = (1.1627 - 0.2308) / 10 = 0.09319$. Thus, the estimated sample size for study A is 46.

Studies B and C are observational investigations on subjects referred for PSG as required by their medical condition and which fulfill the inclusion/exclusion criteria described previously. The number of subjects will be calculated accordingly to the results of the pre-study (group A).

Study D is an observational prospective investigation conducted on unselected consecutive patients without recruitment restrictions, in order to validate the KCG on the real population. Since we do not know how many patients will be necessary for the validation of our screening device, we speculate a size simple of 100 subjects.

Because the KCG device is not intrusive, we do not anticipate difficulties in the recruitment. Our study will not affect in any manner the regular medical care of the patients admitted to the sleep laboratory. The present research proposal is in line with my promotor's expertise, [name], [name] and [name], in the study of sleep physiology (59-63), and sleep apnea (60, 61):

4. Perspectives

As explained above, SDB is a widespread disease with detrimental health effects and its prevalence is supposed to increase in the future years, as the result of the obesity pandemic in an ageing population. PSG is the gold standard for the diagnosis of sleep related disorders but it is an expensive, uncomfortable and time-consuming tool, limiting its use in the daily clinical practice, despite the high prevalence of SDB. Several home sleep tests have been proposed to screen patients suspected for SDB, but they disclose several limitations and are not recommended for patients with cardiovascular, respiratory, metabolic or neurologic co-morbidities (50). We strongly believe that the less cumbersome (57-60) KCG will screen patients for SDB accurately. One of its unique features (57-60) is also that it can directly identify the consequences of SDB and nCPAP therapy on the cardiovascular system, and in especially the presence of frequently associated cardiac arrhythmias (44). With a more efficient pre-screening, those who are most likely to be eligible for nCPAP therapy will have a better access to the currently existing sleep laboratory facilities. To summarize, we aim 1) to propose a new screening tool for patients at risk of SDB, 2) to stratify patients with SDB for adverse cardiovascular events, and 3) to highlight new physio-pathological aspect of sleep apnoea. The present research project has thus the potential of improving sleep apnoea patients care and health, at no additional societal costs.

5. References

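### Group A: KCG is tuned for sensitivity and specificity, but the only validation measure stated is number and duration of apnoeas, which alone does not test the accuracy hypothesis

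*Protocol*

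**What the plan says.** The main hypothesis in section 2 of the Protocol is that "KCG provides sensitive and accurate measures of obstructive and central apnoea as compared to state-of-the-art polysomnography".

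The Group A paragraph under the main hypotheses describes two steps in healthy subjects:

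- **Tuning.** There is a "fine tuning period of the KCG signal post processing to maximise the sensitivity and specificity of voluntary apnoea detection in health subjects".
- **Validation.** In 46 volunteers a computer program issues, in random order, instructions for normal breathing, end-expiratory breath holds (standing in for central apnoea) and Mueller manoeuvres (standing in for obstructive apnoea). The measure is then given: "The number and duration of voluntary central and obstructive apnoea will be assessed in the KCG recordings, not knowing how many were actually generated".

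Sensitivity and specificity are not named again for Group A. The paragraph gives no rule for matching events, no agreement statistic and no criterion for success. It does list ventilation and end-tidal CO2 among the signals recorded at the same time.

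Section 3 sizes Group A on a third quantity: "The parameter taken into consideration for sample size calculation in this group is the total (linear and rotational) systolic kinetic energy of the SCG", taken as a ratio of mean to standard deviation (H). The same section says that Groups B and C will be sized from the Group A results. The Group D paragraph says: "After validation of the three previous steps, we plan to extend the recordings on 100 unselected consecutive patients".

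**The concern.** The tuning target and the main hypothesis both concern whether single events are detected and correctly typed. The stated validation measure does not.

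The number of central apnoeas read from KCG is the sum of three things: central events correctly called, obstructive events called central, and normal breathing called central. It can equal the generated number when all three parts are wrong. Mistyping is the error that matching counts hide best, and separating central from obstructive apnoea is a property that section 2 claims for KCG.

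Duration helps only in part. The duration of an event can be read only if KCG called the event, so missed events drop out of any per-event duration error. Total apnoea time per type does fall with each miss, but false events can refill it.

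Group A is the first of the steps on which the later groups build. A result given only as number and duration would pass forward no event-level accuracy.

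**Working it through.** **The plan's own figure.** Inputs from section 3: Z values 1.96 and 1.64, σ = 0.1247, Δ = (1.1627 − 0.2308)/10 = 0.09319.

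n = 2 × (1.96 + 1.64)² × 0.1247² / 0.09319² = 46.4, stated as 46.

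The figure reproduces. It concerns H, so it says nothing on how precisely counts, sensitivity or specificity will be estimated.

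**Assumed session.** The protocol does not give the number of manoeuvres per volunteer. I assume 10 central, 10 obstructive and 20 normal-breathing periods, with independent errors, in 46 volunteers.

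**(a) Mistyping only, 30% in each direction.** Count of one type = Bin(10, 0.7) + Bin(10, 0.3).
- Mean error: 7 + 3 − 10 = 0
- Variance per volunteer: 2.1 + 2.1 = 4.2
- Standard error of the mean: √(4.2/46) = 0.30
- Correct typing: 70%
- Limits of agreement per volunteer: ±1.96 × √4.2 = ±4.0 events

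**(b) 30% of each type missed, and 15% of normal periods falsely called each type.** Count = Bin(10, 0.7) + Bin(20, 0.15).
- Mean error: 7 + 3 − 10 = 0
- Variance per volunteer: 2.1 + 2.55 = 4.65
- Standard error of the mean: √(4.65/46) = 0.32
- Sensitivity: 70%
- Specificity over normal periods: 1 − 2 × 0.15 = 70%
- Limits of agreement per volunteer: ±1.96 × √4.65 = ±4.2 events

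**(c) Exact cancellation in one session.** With 4 misses and 4 false events per type, the reported counts are 10 and 10. Sensitivity is 6/10 = 60% and specificity is (20 − 8)/20 = 60%. With 4 central and 4 obstructive events swapped, the counts are again 10 and 10, and correct typing is 60%. If every session were like this, the counts would show no spread at all.

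**(d) Labels unrelated to the signal, drawn at the true frequencies.** Expected count per type is 40 × 0.25 = 10, so the mean error is 0. The standard deviation is √(40 × 0.25 × 0.75) = 2.7 events per session. Type-specific sensitivity is 25%.

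**(e) Errors that do not balance.** With 30% missed and false-call rate f per type, the mean count error is −3 + 20f:

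| f per type | Mean count error | Specificity (1 − 2f) |
|---|---|---|
| 0.15 | 0 | 70% |
| 0.05 | −2 | 90% |
| 0 | −3 | 100% |

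At f = 0.05 the standard error is √((2.1 + 0.95)/46) = 0.26, so a bias of −2 would be plain. Mean counts are blind only where misses, false calls and mistypings roughly offset each other.

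**The case against.** The strongest reply is that the paragraph does not limit the analysis to totals. The tuning sentence leads straight into the validation, so the natural intent may be to validate the same property. The sentence on number and duration says what the masked reader extracts and names no test. Masking the reader to how many events were generated is blinding, not an analysis rule. Marking a duration needs a start and an end for each event, so the reading already yields data that could be matched. The matching rule and tables could also sit in a statistical analysis plan that is not at hand. All of this stands. It narrows the point to the measure as worded, which is still not the one that was tuned or hypothesised.

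A reader might infer that validation rests on comparing mean counts, and that a poor detector would therefore pass. The document does not support that:

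- It states neither a mean-count comparison nor a pass rule.
- The only agreement method it names is Bland-Altman, for Group B. Applied per volunteer, it would show limits of about ±4 events on a true count of 10 in (a) and (b). That spread would be a warning, though it could not tell cancelling errors from counting noise or give sensitivity, specificity or typing.
- The rates in (a) and (b) were chosen to cancel exactly, and (e) shows that unbalanced errors are visible.

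The consequences are also limited. Nothing says that apnoea counts drive the sizes of Groups B and C; the only sizing parameter named is H. Group B compares KCG with simultaneous PSG, with attention to obstructive, central and mixed events, so typing is checked before Group D.

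Finally, the protocol does not say that the program's timing is stored, and the time of an instruction is not the time of the manoeuvre.

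**Conclusion.** The point holds in a limited form. Group A is tuned on sensitivity and specificity, the hypothesis is that "KCG provides sensitive and accurate measures of obstructive and central apnoea", and the only measure stated for the validation is number and duration by type. That measure alone does not test the hypothesis, because counts can agree while events are missed, falsely called or mistyped.

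Under the assumed 10/10/20 session with balanced 30% errors, the mean count error is 0 with a standard error of 0.30 to 0.32, while sensitivity or correct typing is 70%. The same assumptions give per-volunteer limits of about ±4 events, so the disagreement would not be wholly invisible. The size depends on the assumed session and on errors that balance. It is not shown that a poor detector would be declared valid. The sample size of 46 is not in question here.

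**What to change.** State in the Group A paragraph that the masked KCG reading will be matched event by event to the program's generated sequence. Confirm the timing of the manoeuvres actually performed from the ventilation and end-tidal CO2 signals already recorded, so that a late or failed manoeuvre is not charged to the detector.

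Report, with confidence intervals clustered by volunteer:

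- sensitivity for central and for obstructive periods;
- specificity over normal-breathing periods;
- the 3x3 table of generated against read state (normal, central, obstructive).

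Keep number and duration as descriptive measures, and show duration error beside the share of events not detected.

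The change needs no further volunteers or recordings. It costs a change of wording, a little more analysis and the need to keep the program's timing. The accuracy figures may look less favourable than agreement on counts.

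### Does Group A score KCG against instructions that volunteers may not have followed, leaving the recorded ventilation signal unused?

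*Protocol*

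**What the plan says.** The Group A text under Main hypotheses (section 2, Aims and hypothesis tested) makes four relevant statements.

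- A tuning period comes first, whose purpose is "to maximise the sensitivity and specificity of voluntary apnoea detection in health subjects". The 46-volunteer study, called the first validation study, follows it.
- In that study "a computer program will generate random instructions of periods of normal breathing", of end-expiratory breath holds (the stand-in for central apnoea) and of Muller's manoeuvres (the stand-in for obstructive apnoea).
- On reading the signal, the number and duration of both kinds of voluntary apnoea "will be assessed in the KCG recordings, not knowing how many were actually generated by the computer program".
- Other signals are recorded alongside, among them "beat to beat non-invasive blood pressure (Finometer), humeral blood pressure (Dinamap), ventilation" and end-tidal CO₂. Neither this text nor section 3 (Methods) says what they are for.

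The background section on sleep disordered breathing describes the disease: "Sleep apnoea syndrome is a common chronic respiratory disease characterised by cyclic airflow cessations during sleep". It describes the central type as "central, where the airflow cessation arise from a central lack in driving to the breathing muscles with no compensatory respiratory efforts".

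The main hypothesis in section 2 names polysomnography as the comparator. Polysomnography is planned for Groups B to D and is not listed among the Group A recordings.

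**The concern.** A validation study needs a reference that shows what really happened. An instruction shows only what was requested. A volunteer may skip a manoeuvre, break it off, start or stop late, or hold the breath unprompted. The only candidate reference in the Group A text is the program's output, and it appears only inside the blinding sentence. The recorded signals that could show whether breathing stopped, and for how long, are listed without a role.

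If KCG were scored against raw instructions, three errors would follow:

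- omitted manoeuvres would count as missed detections;
- unprompted breath holds would count as false alarms;
- unequal delays at start and stop would bias the measured duration.

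Detector error and volunteer compliance would then be mixed in the first validation result.

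**Working it through.** **1. The plan's own figure.** Section 3 sizes study A with 2(Zα + Z1−β)²σ²/Δ², where Zα = 1.96, Z1−β = 1.64, σ = 0.1247 and Δ = (1.1627 − 0.2308)/10 = 0.09319.

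2 × (3.60)² × 0.1247² / 0.09319² = 25.92 × 0.015550 / 0.0086844 = 46.4, against the stated 46.

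The inputs are the mean and spread of H, a ratio computed from the SCG signal. Detection accuracy does not enter, so the choice of reference for detection cannot move this number.

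**2. What scoring against raw instructions would do.** Let f be the share of instructed manoeuvres not performed, and g the share of normal-breathing periods that contain an unprompted apnoea. The protocol gives neither, so every value below is assumed.

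Apparent sensitivity = Se(1 − f) + (1 − Sp)f

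Apparent specificity = Sp(1 − g) + (1 − Se)g

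The example inputs Se = 0.98 and Sp = 0.94 are those the background cites for an earlier mattress-sensor BCG study: "Detection of these events was nevertheless achieved with a sensitivity of 98%, a specificity of 94%, and an accuracy of 98"%.

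| Assumed share | Se = Sp = 1 | Se = 0.98, Sp = 0.94 |
|---|---|---|
| f = 5% | sensitivity 95% | 0.931 + 0.003 = 93.4% |
| f = 10% | sensitivity 90% | 0.882 + 0.006 = 88.8% |
| f = 20% | sensitivity 80% | 0.784 + 0.012 = 79.6% |
| g = 2% | specificity 98% | 0.9212 + 0.0004 = 92.2% |
| g = 5% | specificity 95% | 0.893 + 0.001 = 89.4% |

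In every row the device looks worse than it is.

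For duration, the event minus the instruction equals stop delay minus start delay. On an assumed 20 s instruction:

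- both 1 s late: 0 s;
- start 2 s late, stop on time: −2 s (−10%);
- start on time, stop 2 s late: +2 s (+10%).

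**3. Whether the protocol commits to that scoring.** Three comparisons of the text show that it does not.

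- *Blinding against reference.* The sentence states what the KCG reader must not know. It names no comparator. At most it implies that the reader's count will later be set beside the program's count. For duration it implies nothing, so the duration calculation above tests a rule that the protocol does not contain.
- *Metric.* Sensitivity and specificity are named for the tuning period. For the 46 volunteers the quantities named are number and duration. The table uses a per-period metric that the protocol does not define for this study.
- *Definition.* The airflow description in the background concerns a disease during sleep. Group A uses voluntary manoeuvres that the protocol calls surrogates. The two texts are not linked, and they do not conflict.

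**4. Whether the data would be lost.** They would not. Ventilation and end-tidal CO₂ are on the list of Group A recordings. Confirming that a manoeuvre took place, and marking its start and end, needs no new measurement.

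**The case for a change.** The strongest reply is that the reference standard is a core design element of a validation study, which a protocol should not leave to be inferred. Where the Group A text points at all, it points to the program's output. The background mentions an earlier volunteer study of breath holds done with an oral-nasal flow detector, so the authors knew of the approach. A bias that understates accuracy still gives a wrong answer, and duration error can go either way. Group D is also to start only after the earlier steps have been validated.

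Part of this stands. The role of the ventilation signal is not stated, and stating it would make the protocol clearer. But the reply treats a missing sentence as if it were a rule. The text does not say that an unperformed manoeuvre counts as a missed detection. Marking manoeuvres on recorded traces is a scoring detail that a statistical analysis plan or scoring manual usually holds.

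Nor would naming ventilation as the reference be a sure gain. The protocol does not say what the ventilation sensor measures. If it follows chest movement rather than airflow, the effort in a Muller's manoeuvre could register as breathing, and the signal would be a poor reference for the obstructive surrogate. Even an airflow signal could not separate the two surrogates, because by the protocol's own description they differ in respiratory effort. The instruction would remain the label for type in either case.

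**Conclusion.** No change to the plan is called for. The protocol leaves a gap, namely the unstated use of signals it already records, and analysts can fill that gap sensibly. It does not fix a rule that gives a wrong result.

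The size is unknown from the document. The illustrated losses of sensitivity and specificity hold only if KCG is scored against raw instructions and if the assumed rates apply; the protocol states neither. At event level the error would lower the device's apparent accuracy. The sample size of 46, the main hypothesis against polysomnography and the comparisons in Groups B to D do not depend on it. Section 3 sizes studies B and C from the results of Group A, but does not say that detection accuracy is the result to be used.

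This conclusion assumes that the ventilation recording can be time-aligned with KCG and shows airflow well enough to confirm a manoeuvre. If it does not, naming it as the reference in the protocol would not help either.
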